1.23 Rationale for Endpoints

The proposed primary and secondary efficacy endpoints conform to recommended consensus definitions of the International Society for Cutaneous Lymphomas (ISCL), the United States Cutaneous Lymphoma Consortium (USCLC), and the Cutaneous Lymphoma Task Force of the European Organization for Research and Treatment of Cancer (EORTC) and will permit a relative comparison to other published work using these definitions.

The Primary efficacy endpoint will be the overall cutaneous response rate at week 27 by the Modified Skin Severity Assessment (mSWAT) score.

The mSWAT is calculated using body surface area (BSA) of each MF lesion (palm plus fingers of the patient $\approx 1\%$ BSA) in each of 12 areas of the body, multiplying the sum of the BSA of each lesion type by a weighting factor (patch=1, plaque=2, and tumor =4) and generating a sum of the subtotals of each lesion subtype.

Hypothesis: Biopsies in MF reveal an abnormal accumulation of clonal CD4+ helper T-cells initially in the epidermis and later in the dermis and subcutis. There is also a characteristic anti-tumor host response of infiltrating CD8+/TIA-1+ cytotoxic T-lymphocytes in lesional skin. Histologically, the intensity of this infiltrate diminishes with disease progression from patch, plaque to tumor disease and has been postulated to reflect the suppressive effects of TH2 cytokine production and CD25+ TReg phenotypic induction by the malignant CD4+ T-cells (Phillips et al., 2016; Rozati et al., 2016).

Pembrolizumab is a humanized monoclonal IgG4 antibody directed against the receptor PD-1 (programmed cell death-1) expressed on the surface of activated T cells (Nguyen et al., 2017; Warren et al., 2017).

We hypothesize PD-1 inhibition will preserve and enhance the anti-tumor responses in MF through effector T cell activation and TReg inhibition. (Wang et al., 2018)

We have also conducted a preliminary analysis of PD-1/CD279 expression in a representative group of patch, plaque, and tumor MF biopsy specimens and found expression in nearly all cases; this finding further supports the hypothesis that pembrolizumab may have value in the management of all stages of MF.

1.3 Correlative Research

- 1.31 This study proposes to characterize the histologic features of the anti-tumor host response before and after treatment with pembrolizumab. Prior to the initial dose of pembrolizumab, a 6 mm punch skin biopsy of the most common presenting morphology (i.e. patch, plaque, or tumor) will be obtained for each study participant; at the second cycle (week 6), an additional 6 mm punch skin biopsy of the same morphologic type will be obtained. Immunohistochemistry will then be used to assess the levels of CD4, CD8, PD-1/CD279, and PD-L1 expression before and after treatment with pembrolizumab.

2.0 Goals**2.1 Primary Goal**

To evaluate the antitumor activity of pembrolizumab in patients with advanced MF as initial systemic therapy.

2.2 Secondary Goals

2.21 To evaluate safety of pembrolizumab in this patient population.

2.22 To evaluate response rates of pembrolizumab in this patient population.

2.23 To determine the progression free survival, duration of response, time to response and overall survival of pembrolizumab in this patient population .

2.3 Correlative Research

To characterize the histologic features of the anti-tumor response in patients with advanced MF before and after treatment with pembrolizumab.

3.0 Registration Patient Eligibility

3.1 Registration – Inclusion Criteria

3.11 Age \geq 18 years.

3.12 Histological confirmation of one of the following:

- Stage IIB-IV Mycosis Fungoides not previously treated with systemic therapy
- Stage IB/IIA Mycosis Fungoides with mSWAT \geq 20 with high risk morphologic features defined as thick plaque disease and/or follicular involvement who have failed one form of skin-directed therapy.
- Sézary Syndrome patients not previously treated with systemic therapy.

3.13 Measurable disease based on mSWAT and/or RECIST 1.1 (see Section 11.0).

3.14 Be willing to provide tissue from a newly obtained core or excisional biopsy of a tumor lesion. Note: Newly-obtained is defined as a specimen obtained up to 6 weeks (42 days) prior to registration. Exception: Subjects for whom newly-obtained samples cannot be provided (e.g. inaccessible or subject safety concern) may submit an archived specimen only upon agreement from the Sponsor.

3.15 ECOG Performance Status (PS)0 or 1 ([Appendix I](#)).

3.16 The following laboratory values obtained \leq 28 days prior to registration.

- Absolute neutrophil count (ANC) \geq 1,500 /mcL
- Platelet count \geq 100,000/mcL
- Hemoglobin \geq 9.0 g/dL or \geq 5.6 mmol/L without transfusion or EPO dependency (within 7 days of assessment)
- Serum total bilirubin \leq 1.5 X ULN OR Direct bilirubin \leq ULN for subjects with total bilirubin levels $>$ 1.5 ULN
- Aspartate transaminase (AST) and Alanine transaminase (ALT) \leq 2.5 X ULN OR \leq 5 X ULN for subjects with liver metastases
- Albumin $>$ 2.5 mg/dL
- Serum creatinine \leq 1.5 x upper limit of normal (ULN) OR Measured or calculated creatinine clearance \geq 60 ml/min for subject with creatinine levels $>$ 1.5 x institutional ULN.
- PT/INR and PTT \leq 1.5 X ULN OR if patient is receiving anticoagulant therapy and PT/INR or PTT is within therapeutic range of intended use of coagulants

3.17 Negative urine or serum pregnancy test done \leq 28 days prior to registration and \leq 72 hours prior to receiving the first dose of study medication, for women of childbearing potential only.

3.18 Female subjects of childbearing potential must be willing to use an adequate method of contraception for the course of the study through 120 days after the last dose of the study medication.

Note: Abstinence is acceptable if this is the usual lifestyle and preferred contraception for the subject

3.19 Male subjects of childbearing potential must agree to use an adequate method of contraception for the course of the study through 120 days after the last dose of the study medication.

Note: Abstinence is acceptable if this is the usual lifestyle and preferred contraception for the subject

3.20a Provide written informed consent.

3.20b Willing to return to enrolling institution for follow-up (during the Active Monitoring Phase of the study).

3.20c Willing to provide tissue samples for correlative research purposes (see Section 17).

3.2 Registration – Exclusion Criteria

3.21 Any of the following because this study involves:

an agent that has known genotoxic, mutagenic and teratogenic effects:

- Pregnant women
- Nursing women
- Men or women of childbearing potential who are unwilling to employ adequate contraception

3.22 Is currently participating and receiving study therapy or have participated in a study of an investigational agent and received study therapy or used an investigational device <= 4 weeks prior to registration.

3.23 Has a diagnosis of immunodeficiency or is receiving systemic steroid therapy or any other form of immunosuppressive therapy <= 7 days prior to registration.

3.24 Has a known history of active TB (Bacillus Tuberculosis).

3.25 Hypersensitivity to pembrolizumab or any of its excipients.

3.26 Has had a prior anti-cancer monoclonal antibody (mAb) <= 4 weeks prior to registration or who has not recovered (i.e., \leq Grade 1 or at baseline) from adverse events due to agents administered more than 4 weeks earlier.

3.27 Has had prior chemotherapy, targeted small molecule therapy, or radiation therapy <= 2 weeks prior to registration or who has not recovered (i.e., \leq Grade 1 or at baseline) from adverse events due to a previously administered agent.

- Note: Subjects with \leq Grade 2 neuropathy are an exception to this criterion and may qualify for the study.
- Note: If subject received major surgery, they must have recovered adequately from the toxicity and/or complications from the intervention prior to starting therapy.

3.28 Has a known additional malignancy that is progressing or requires active treatment. Exceptions: basal cell carcinoma of the skin or squamous cell carcinoma of the skin that has undergone potentially curative therapy or in situ cervical cancer.

3.29 Has known active central nervous system (CNS) metastases and/or carcinomatous meningitis. Exceptions: subjects with previously treated brain metastases may participate provided they are stable (without evidence of progression by imaging <= 4 weeks prior to registration and any neurologic symptoms have returned to baseline), have no evidence of new or enlarging brain

metastases, and are not using steroids for at least \leq 7 days prior to registration. This exception does not include carcinomatous meningitis which is excluded regardless of clinical stability.

- 3.30 Has active autoimmune disease that has required systemic treatment in the past 2 years (i.e. with use of disease modifying agents, corticosteroids or immunosuppressive drugs). Note: Replacement therapy (eg., thyroxine, insulin, or physiologic corticosteroid replacement therapy for adrenal or pituitary insufficiency, etc.) is not considered a form of systemic treatment.
- 3.31 Has a history of non-infectious pneumonitis that required steroids or has current pneumonitis.
- 3.32 Has an active infection requiring systemic therapy.
- 3.33 Has a history or current evidence of any condition, therapy, or laboratory abnormality that might confound the results of the trial, interfere with the subject's participation for the full duration of the trial, or is not in the best interest of the subject to participate, in the opinion of the treating investigator.
- 3.34 Has known psychiatric or substance abuse disorders that would interfere with cooperation with the requirements of the trial.
- 3.35 Is pregnant or breastfeeding, or expecting to conceive or father children within the projected duration of the trial, starting with the screening visit through 120 days after the last dose of trial treatment.
- 3.36 Has received prior therapy with an anti-PD-1, anti-PD-L1, or anti-PD-L2 agent.
- 3.37 Has a known history of Human Immunodeficiency Virus (HIV) (HIV 1/2 antibodies).
- 3.38 Has known active Hepatitis B (e.g., HBsAg reactive) or Hepatitis C (e.g., HCV RNA [qualitative] is detected).
- 3.39 Has received a live vaccine \leq 30 days prior to registration.

Note: Seasonal influenza vaccines for injection are generally inactivated flu vaccines and are allowed; however intranasal influenza vaccines (e.g., Flu-Mist®) are live attenuated vaccines, and are not allowed.
- 3.39a Sezary syndrome patients with high blood burden requiring immediate cytoreduction.

4.0 Test Schedule

4.1 Test schedule for Mycosis Fungoïdes

Tests and procedures	≤ 28 days prior to registration	Active Monitoring Phase*			Follow-up*	
		prior to treatment Day 1, Cycles 2-4 ⁷	prior to treatment Day 1, Cycles 5 and beyond ⁷	End of treatment (21 days after last dose)	Clinical Follow- up (30 days after EOT)	Clinical Follow- up visit (90 days after EOT)
Main study Informed Consent	X					
Inclusion/Exclusion Criteria	X					
Demographics, medical history	X				X	
Ht and Wt**	X	X		X		
Vital signs						
Blood pressure	X	X	X	X		
Pulse						
Temperature						
Prior and Concomitant Medication Review	X				X	
Post-study Anticancer therapy status					X	X
Adverse event assessment	X	X	X	X	X	X
Physical Exam	X	X	X	X		
Dermatology Exam ^R	X	X	X	X	X	X
Standardized Clinical Photography ^R	X	X	X	X	X	X
Skin Biopsy	X	X ^R				
ECOG PS	X			X		X
mSWAT	X	X	X	X	X	X
Pregnancy test ¹	X					
Hematology group						
CBC with Diff	X	X	X	X	X	
Chemistry group ²	X	X	X	X	X	
Urinalysis	X					
PT/INR and PTT	X					
T3, FT4, and TSH ³	X	X	X	X	X	
Tumor Imaging ⁴	X		X	X		
T and B-cell Quantitation ⁵	X		X ^R	X ^R		
Mandatory Research tissue specimens (see Section 17.0) ^{6,R} ,	X	X				

Cycle = 21 days

***Window for all visits = ± 3 days**

1. For women of childbearing potential only. Must be done ≤ 72 hrs prior to treatment and if clinically

indicated.

2. Chemistry panel: Albumin, total bilirubin, direct bilirubin, calcium, carbon dioxide (bicarbonate), chloride, creatinine, glucose, alkaline phosphatase, potassium, total protein, sodium, aspartate amino transferase (AST) (SGOT), alanine amino transferase (ALT) (SGPT), urea nitrogen (BUN)
3. Repeat every other cycle starting on Day 1, Cycle 2.
4. Whole body CT/PET. 1 Week after the end of Cycle 4 during course of treatment and then, at the End of Treatment Visit.
5. 1 Week after the end of Cycle 4 during course of treatment and then, at the End of Treatment Visit.
6. Tissue specimens (Skin Biopsy) will be collected and submitted after registration and Cycle 2, Day 15 only. (See Section 17.0)
7. Cycle 1 day 1 prior to treatment is recorded as baseline, Prior to treatment Day 1 Cycles 2-4 is recorded in the data base as end of cycles 1-3, Prior to treatment Day 1 Cycles 5 and beyond is recorded in the database as end of cycle 4 and beyond.

**Ht not required after registration.

R Research funded (see Section 19.0)

4.2 Survival Follow-up

	Survival Follow-up				
	q. 3 months until PD	At PD	After PD q. 3 months	Death	New Primary
Survival Follow-up	X	X	X	X	At each occurrence

1. If a patient is still alive 2.5 year after registration, no further follow-up is required.

5.0 Stratification Factors OR Grouping Factor:

None.

6.0 Registration Procedures

6.1 Registration:

6.11 Registering a patient

To register a patient, access the Mayo Clinic Cancer Center (MCCC) web page and enter the registration/randomization application. The registration/randomization application is available 24 hours a day, 7 days a week. Back up and/or system support contact information is available on the website. If unable to access the website, call the MCCC Registration Office at [REDACTED] between the hours of 8 a.m. and 4:30 p.m. Central Time (Monday through Friday).

The instructions for the registration/randomization application are available on the MCCC web page [REDACTED] and detail the process for completing and confirming patient registration. Prior to initiation of protocol treatment, this process must be completed in its entirety and an MCCC subject ID number must be available as noted in the instructions. It is the responsibility of the individual registering the patient to confirm the process has been successfully completed prior to release of the study agent. Patient registration via the registration/randomization application can be confirmed in any of the following ways:

- Contact the MCCC Registration Office [REDACTED] If the patient was fully registered, the MCCC Registration Office staff can access the information from the centralized database and confirm the registration.
- Refer to “Instructions for Remote Registration” in section “Finding/Displaying Information about A Registered Subject.”

6.2 Verification of materials

Prior to accepting the registration, registration/randomization application will verify the following:

- IRB approval at the registering institution
- Patient eligibility
- Existence of a signed consent form
- Existence of a signed authorization for use and disclosure of protected health information

6.3 Documentation of IRB approval

Documentation of IRB approval must be on file in the Registration Office before an investigator may register any patients.

In addition to submitting initial IRB approval documents, ongoing IRB approval documentation must be on file (no less than annually) at the Registration Office (fax: [REDACTED]). If the necessary documentation is not submitted in advance of attempting patient registration, the registration will not be accepted and the patient may not be enrolled in the protocol until the situation is resolved.

When the study has been permanently closed to patient enrollment, submission of annual IRB approvals to the Registration Office is no longer necessary.

6.4 Correlative Research

A mandatory correlative research component is part of this study, the patient will be automatically registered onto this component (see Sections 17.1).

6.5 Treatment on protocol

Treatment on this protocol must commence at Mayo Clinic Florida under the supervision of a dermatologist and medical oncologist.

6.6 Treatment start

Treatment cannot begin prior to registration and must begin ≤ 28 days after registration.

6.7 Pretreatment

Pretreatment tests/procedures (see [Section 4.0](#)) must be completed within the guidelines specified on the test schedule.

6.8a Baseline symptoms

All required baseline symptoms (see [Section 10.6](#)) must be documented and graded.

6.8b Study drug

Study drug is available on site.

6.8c Study Conduct

The clinical trial will be conducted in compliance with regulations (21 CFR 312, 50, and 56), guidelines for Good Clinical Practice (ICH Guidance E6), and in accordance with general ethical principles outlined in the Declaration of Helsinki; informed consent will be obtained from all participating patients; the protocol and any amendments will be subject to approval by the designated IRB prior to implementation, in accordance with 21 CFR 56.103(a); and subject records will be stored in a secure location and subject confidentiality will be maintained. The investigator will be thoroughly familiar with the appropriate use of the study drug as described in the protocol and Investigator's Brochure. Essential clinical documents will be maintained to demonstrate the validity of the study and the integrity of the data collected. Master files should be established at the beginning of the study, maintained for the duration of the study and retained according to the appropriate regulations.

7.0 Protocol Treatment

7.1 Treatment Schedule

Agent	Dose	Route	Day	Cycles
Pembrolizumab	200 mg	IV	Day 1	q3 weeks until disease progression, intolerable toxicity, or CR for a maximum duration of 24 months

Protocol treatment should be administered on Day 1 of each cycle after all procedures/assessments have been completed as detailed on the Test Schedule (Section 4.0). Trial treatment may be administered up to 3 days before or after the scheduled Day 1 of each cycle due to administrative reasons.

All trial treatments will be administered on an outpatient basis.

Pembrolizumab 200 mg will be administered as a 30 minute IV infusion every 3 weeks. Sites should make every effort to target infusion timing to be as close to 30 minutes as possible. However, given the variability of infusion pumps from site to site, a window of -5 minutes and +10 minutes is permitted (i.e., infusion time is 30 minutes: -5 min/+10 min).

The Pharmacy Manual contains specific instructions for the preparation of the pembrolizumab infusion fluid and administration of infusion solution.

8.0 Dosage Modification Based on Adverse Events

Strictly follow the modifications in this table for the first **two** cycles, until individual treatment tolerance can be ascertained. Thereafter, these modifications should be regarded as guidelines to produce mild-to-moderate, but not debilitating, side effects. If multiple adverse events are seen, administer dose based on greatest reduction required for any single adverse event observed. Reductions or increases apply to treatment given in the preceding cycle and are based on adverse events observed since the prior dose.

→ **ALERT:** *ADR reporting may be required for some adverse events (See Section 10.0)* ←

→ → ***Use the NCI Common Terminology Criteria for Adverse Events (CTCAE) current version 5.0****
unless otherwise specified ← ←

* Located at [REDACTED]

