8.1 Dose Modifications Based on Adverse Events

CTCAE System/Organ/Class (SOC)	ADVERSE EVENT	AGENT	ACTION**
Cardiac disorders	Myocarditis	pembrolizumab	Hold if grade 1 or 2. Administer corticosteroids as clinically indicated. Discontinue if Grade 3 or 4. Pembrolizumab should be permanently discontinued if AE does not resolve within 12 weeks of last dose or corticosteroids cannot be reduced to ≤ 10 mg prednisone or equivalent per day within 12 weeks and continue to survival follow-up.
Endocrine disorders	Hyperthyroidism	pembrolizumab	Continue if grade 2. Treat with non-selective beta-blockers (e.g. propranolol) or thionamides as appropriate. ¹ Hold or discontinue if grade 3 or 4. If discontinue, continue to survival follow-up. Pembrolizumab should be permanently discontinued if AE does not resolve within 12 weeks of last dose and continue to survival follow-up.
	Hypophysitis	pembrolizumab	Hold if grade 2. Administer corticosteroids and initiate hormonal replacements as clinically indicated. ¹ Hold or discontinue if grade 3 or 4. Pembrolizumab should be permanently discontinued if AE does not resolve within 12 weeks of last dose or corticosteroids cannot be reduced to ≤ 10 mg prednisone or equivalent per day within 12 weeks and continue to survival follow-up.
	Hypothyroidism	pembrolizumab	Continue if grade 2-4. Initiate thyroid replacement hormones (e.g. levothyroxine or liothyroinine) per standard of care. Pembrolizumab should be permanently discontinued if AE does not resolve within 12 weeks of last dose and continue to survival follow-up.

CTCAE System/Organ/Class (SOC)	ADVERSE EVENT	AGENT	ACTION**
Gastrointestinal disorders	Diarrhea or Colitis	pembrolizumab	Hold if grade 2-3. Discontinue if Grade 4 or if AE does not resolve within 12 weeks of last dose or inability to reduce corticosteroid to 10 mg or less prednisone or equivalent per day within 12 weeks and continue to survival follow-up.
Immune System disorders	All other immune-related AEs	pembrolizumab	Hold if intolerable/persistent grade 2. Administer corticosteroids as clinically indicated. Hold if grade 3 AE, unless the event is Gullian-Barre Syndrome and/or Encephalitis, then, pembrolizumab should be discontinued. If AE does not resolve within 12 weeks of last dose or corticosteroids cannot be reduced to \leq 10 mg prednisone or equivalent per day within 12 weeks and continue to survival follow-up. Pembrolizumab should be discontinued if grade 4 AE or recurrent grade 3.

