Investigations	AST / ALT elevation or Increased Bilirubin	pembrolizumab	Hold if grade 2. Administer corticosteroids (initial dose of 1-2mg/kg prednisone or equivalent) followed by taper. Discontinue if Grade 3 or 4 or if AE does not resolve within 12 weeks of last dose or inability to reduce corticosteroid to 10 mg or less prednisone or equivalent per day within 12 weeks and continue to survival follow-up.
Metabolism and nutrition disorders	Type 1 diabetes mellitus (T1DM) or Hyperglycemia	pembrolizumab	Hold if Newly onset T1DM or Grade 3 or 4 hyperglycemia associated with evidence of β -cell failure. Initiate insulin replacement therapy for subjects with T1DM. Administer anti-hyperglycemic in subjects with hyperglycemia. Discontinue if AE does not resolve within 12 weeks of last dose and continue to survival follow-up.

CTCAE System/Organ/Class (SOC)	ADVERSE EVENT	AGENT	ACTION**
Renal and urinary disorders	Nephritis	pembrolizumab	Hold if grade 2. Administer corticosteroids (prednisone 1-2mg/kg or equivalent) followed by taper. Discontinue if grade 3 or 4 or if AE does not resolve within 12 weeks of last dose or inability to reduce corticosteroid to 10 mg or less prednisone or equivalent per day within 12 weeks and continue to survival follow-up.
Respiratory, thoracic and mediastinal disorders	Pneumonitis	pembrolizumab	Hold if grade 2. Administer corticosteroids (initial dose of 1-2mg/kg prednisone or equivalent) followed by taper. Discontinue if recurrent grade 2, if grade 3 or 4, or if AE does not resolve within 12 weeks of last dose or inability to reduce corticosteroid to 10 mg or less prednisone or equivalent per day within 12 weeks and continue to survival follow-up.
Skin and subcutaneous tissue disorders	Stevens-Johnson syndrome/ toxic epidermal necrolysis	pembrolizumab	Hold if grade 3. Discontinue if grade 4. Discontinue if AE does not resolve within 12 weeks of last dose and continue to survival follow-up.

** Use the following to describe actions in the Action column:

- **Omit** = The current dose(s) for the specified drug(s) during a cycle is skipped. The patient does not make up the omitted dose(s) at a later time.
- **Hold/Delay** = The current dose(s) of all drugs during a cycle is delayed. The patient does make up the delayed dose(s) when the patient meets the protocol criteria to restart drugs.
- **Discontinue** = The specified drug(s) are totally stopped.

NOTES:

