- ¹Withhold or permanently discontinue pembrolizumab is at the discretion of the investigator or treating physician.
- For subjects with Grade 3 or 4 immune-related endocrinopathy where withhold of pembrolizumab is required, pembrolizumab may be resumed when AE resolves to \leq Grade 2 and is controlled with hormonal replacement therapy or achieved metabolic control (in case of T1DM)

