AEs associated with pembrolizumab exposure may represent an immunologic etiology. These immune-related AEs (irAEs) may occur shortly after the first dose or several months after the last dose of pembrolizumab treatment and may affect more than one body system simultaneously. Therefore, early recognition and initiation of treatment is critical to reduce complications. Based on existing clinical trial data, most irAEs were reversible and could be managed with interruptions of pembrolizumab, administration of corticosteroids and/or other supportive care. For suspected irAEs, ensure adequate evaluation to confirm etiology or exclude other causes. Additional procedures or tests such as bronchoscopy, endoscopy, skin biopsy may be included as part of the evaluation. Based on the severity of irAEs, withhold or permanently discontinue pembrolizumab and administer corticosteroids. Dose modification and toxicity management guidelines for AEs associated with pembrolizumab are provided in the table in Section 8.1.

9.6b Toxicity management of infusion-reactions related to pembrolizumab

Pembrolizumab may cause severe or life threatening infusion-reactions including severe hypersensitivity or anaphylaxis. Signs and symptoms usually develop during or shortly after drug infusion and generally resolve completely within 24 hours of completion of infusion. Dose modification and toxicity management guidelines on pembrolizumab associated infusion reaction are provided in the table below.

NCI CTCAE Grade	Treatment	Premedication at Subsequent Dosing
Grade 1 Mild reaction; infusion interruption not indicated; intervention not indicated	Increase monitoring of vital signs as medically indicated until the subject is deemed medically stable in the opinion of the investigator.	None

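### Section 8.0 makes the 8.1 hold and discontinue rules strict for two cycles only, so from cycle 3 the fixed discontinuation thresholds and the 12-week limits are no longer mandatory

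*Combined protocol and SAP*

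**What the plan says.** Section 8.0 sets the force of the table in Section 8.1. The table is to be followed strictly for two cycles, until the patient's tolerance is known. After that, "Thereafter, these modifications should be regarded as guidelines to produce mild-to-moderate, but not debilitating, side effects". No row, grade or time limit is exempted from the change. A cycle is 21 days (Section 4.1), and treatment may run to 24 months (Section 7.1).

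The table contains specific stops. For pneumonitis: "Discontinue if recurrent grade 2, if grade 3 or 4, or if AE does not resolve within 12 weeks of last dose". For immune-related events without a row of their own: "Pembrolizumab should be discontinued if grade 4 AE or recurrent grade 3". The time limit recurs down the table, typically as discontinuation "if AE does not resolve within 12 weeks of last dose or corticosteroids cannot be reduced to" a low daily prednisone dose within the same 12 weeks.

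Section 9.6a describes the timing of these events: "These immune-related AEs (irAEs) may occur shortly after the first dose or several months after the last dose of pembrolizumab treatment". It adds an instruction that is not tied to any cycle: "Based on the severity of irAEs, withhold or permanently discontinue pembrolizumab and administer corticosteroids". It gives no grades and sends the reader back to the 8.1 table.

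For concurrent events, Section 8.0 says: "If multiple adverse events are seen, administer dose based on greatest reduction required for any single adverse event observed". Section 7.1 fixes the dose at 200 mg, and 8.1 defines no reduction.

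**The concern.** Two cycles would be a sensible strict period if tolerance showed itself by then. For this drug the protocol says otherwise: Section 9.6a expects immune-related events even months after dosing stops, and Section 15.191 repeats the point. The strict period therefore ends before much of the toxicity it is meant to govern can be expected to appear.

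The 8.1 stops are also the only graded stops for immune-related events that act on the individual patient. If they become advisory from cycle 3, whether a given patient stops depends on the investigator's judgement, in a trial where treatment may continue for about two years. What is at stake is patient safety and consistent handling of toxicity, not the efficacy result.

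**Working it through.** **Length of the strict period.** Inputs: two strict cycles (8.0), 21-day cycles (4.1), 24 months maximum (7.1), primary assessment at cycle 9 (16.1).

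- Strict period: 2 × 21 = 42 days.
- Full course: 24 × 30.4375 = 730.5 days, so 42 / 730.5 = 5.7%. With 104 weeks (728 days) the share is 5.8%.
- Cycles in a full course: 730.5 / 21 = 34.8, about 35. Outside the strict period: 35 − 2 = 33, or 33/35 = 94%.
- Up to the primary assessment: cycles 3 to 9, so 7 of 9 = 78%.

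These are shares of the longest possible exposure. Progression, complete response or toxicity ends treatment sooner.

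**What the table makes mandatory while it is strict.**

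| Row in 8.1 | Discontinuation by grade or recurrence | 12-week limit |
|---|---|---|
| Myocarditis | grade 3 or 4 | yes |
| Diarrhea or colitis | grade 4 | yes |
| AST/ALT or bilirubin | grade 3 or 4 | yes |
| Nephritis | grade 3 or 4 | yes |
| Pneumonitis | grade 3 or 4; recurrent grade 2 | yes |
| Stevens-Johnson syndrome / toxic epidermal necrolysis | grade 4 | yes |
| Other immune-related events | grade 4; recurrent grade 3; grade 3 Guillain-Barré syndrome or encephalitis | condition given, no action stated |
| Hyperthyroidism; hypophysitis | grade 3-4 discretionary (footnote 1) | yes |
| Hypothyroidism; type 1 diabetes or hyperglycemia | none | yes |

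Rows: 7 with a non-discretionary stop + 2 discretionary + 2 with the time limit only = 11. The 12-week limit carries an action in 11 − 1 = 10 rows.

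**Can a 12-week limit expire inside the strict period?** The limit is 12 × 7 = 84 days from the last dose. Counting from dose 1 with cycles on schedule, it expires at day 84 after dose 1, day 21 + 84 = 105 after dose 2, and day 42 + 84 = 126 after dose 3. The earliest of these is 84 − 42 = 42 days after the strict period ends. If a held cycle counts as still open, the limit can expire within the strict period after dose 1 or dose 2. After dose 3 or later it falls outside on either count.

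**What else acts on a patient from cycle 3.**

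- The aim stated in 8.0 is a severity aim. It argues against dosing through grade 3-4 events but orders no stop. Recurrent grade 2 pneumonitis is moderate by grade, and the 12-week limits turn on duration and steroid dose, so this aim gives no reason to stop in either case.
- Section 9.6a applies in every cycle but does not say which grade leads to holding and which to stopping.
- Section 7.1 ends treatment for intolerable toxicity, without a grade.
- Section 9.6b has its own stop for grade 3-4 infusion reactions, which covers nothing else.
- The adverse event stopping rule in Section 16.63 suspends accrual, not dosing. It counts only related non-hematologic events of grade 4 or higher. Once the tenth and last patient is enrolled (16.31), it has nothing left to suspend.

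**The case against.** A reader might infer that from cycle 3 an investigator is free to keep dosing through, say, grade 3-4 myocarditis, because all seven rows have lapsed. The documents do not support that. Continuing would conflict with the aim in 8.0, with the 9.6a instruction to withhold or stop by severity, and with the toxicity criterion in 7.1. Nor does the word guidelines settle the matter by itself: 9.6b uses it of a table that plainly orders permanent discontinuation. What remains is the contrast within 8.0 between strict use and what follows. That contrast does loosen something, namely the fixed thresholds and time limits.

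Oversight is also fuller than the accrual rule alone suggests. The statistician reviews adverse events weekly, and the DSMB reviews safety at least twice a year (16.61). Grade 4-5 events called unrelated are checked (16.63), serious grade 4-5 events are reported within 24 hours (10.4), and adverse events bear on any decision to terminate (16.34). This stands, but none of it is a stop for an individual patient.

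Two smaller inferences also go too far. The 6% is a calendar share, not a share of risk: the documents give no event rate by cycle, so the number of affected stops cannot be computed. And the dose-reduction sentence, though it cannot be carried out, does not leave concurrent events without any rule. Each row still applies, and a discontinuation naturally outranks a hold.

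**Conclusion.** The point holds in a bounded form. Section 8.0 states a rule, and its effect is that from cycle 3 the discontinuation thresholds in seven of 11 rows and the 12-week limits are no longer mandatory. For grade 3-4 events the loss is of a fixed threshold, since the plan still leans towards stopping. The clearest losses are the recurrent grade 2 pneumonitis stop and the 12-week limits, where nothing else in the plan supplies a stop.

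The 42 days assume cycles on schedule; holds could lengthen the strict period. At most 10 patients are exposed. The primary endpoint, sample size and error rates are untouched. It should be fixed because the stops concern serious toxicity and the change is cheap.

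**What to change.** 1. In 8.0, replace the first two sentences with: *The hold and discontinue actions in 8.1, including the 12-week limits, apply in every cycle. Footnote 1 discretion is kept. After a hold, the investigator may resume dosing once the event has resolved and corticosteroids are down to a daily prednisone equivalent of 10 mg or less, within the 12-week limit. For endocrinopathies (including type 1 diabetes and hyperthyroidism), an event at grade 2 or lower that is controlled on replacement or medical therapy counts as resolved.*
2. In 8.0, replace the two sentences on dose reductions and increases with: *If several adverse events occur, apply the most restrictive action in 8.1; the dose is not reduced or increased.*
3. In the row for other immune-related events, put *Discontinue* before the 12-week condition.

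The restart rule in edit 1 is needed because no row of 8.1 gives one. The notes give one only for endocrine events ("For subjects with Grade 3 or 4 immune-related endocrinopathy where withhold of pembrolizumab is required, pembrolizumab may be resumed when AE resolves to" grade 2 or lower with control). Without it, binding holds could be read as impossible to lift. The endocrine sentence keeps that grade condition and avoids forced stops for controlled thyroid disease or diabetes. For other events 8.1 does not say which grade counts as resolved; the sponsor should state it in the same edit.

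Cost: a small loss of investigator discretion after cycle 2, since a patient who is benefiting may have to stop under a rule that could now be set aside, and an amendment that needs IRB approval (6.8c). Visits, data collection and the statistical design do not change.
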